5.0 Treatment Plan

5.1 **General:** All patients should be registered with PDMS. Information pertaining to important prognostic factors such as age, performance status and prior therapy will be recorded.

5.2 **Treatment Schedule:** (Each cycle is approximately 28-35 days)

a. **Phase I**

Nivolumab dosed as indicated below starting approximately on day 24 ± 2 days

Idarubicin 12 mg/m² IV over 15 to 30 minutes daily x 3 (days 1-3)

ara-C 1.5 g/m² IV over 24 hours daily (days 1-4)

Solumedrol 50 mg or dexamethasone 10 mg IV daily for 3-4 days with ara-C (days 1-4)

All patients may receive a second induction course at the discretion of treating physician.

The dose of investigational agent, that is, Nivolumab, will be escalated in successive cohorts of patients. Patients will be entered sequentially to each dose level. If none of the first 3 patients at a dose level experience first cycle dose-limiting toxicity (DLT), new patients may be entered at the next higher dose level. If 1 of 3 patients experience first cycle DLT, up to 3 more patients are started at that same dose level. If 1 of 6 experience DLT, then new patients may be entered at the next higher dose level. If 2 or more experience first cycle DLT, no further patients are started at that dose. The MTD is the highest dose level in which <2 patients of 6 develop first cycle DLT. The following table lists out the 3 dosage levels that will be used in the study, and the starting dose is 1mg/kg IV of Nivolumab. There will be no intra-patient dose escalation for Nivolumab.

The enrollment of participants will be staggered; all the participants in each cohort will be observed for approximately 3 weeks from the first dose of Nivolumab before proceeding to the next cohort.

Dose of nivolumab will be as follows:

Dose level	Nivolumab (mg/kg IV)	No of patients
-1	0.3	3
0	1	3
1	3	3

b. **Phase II** (Each cycle is approximately 28-35 days)

Patients will receive 1 or 2 induction cycles of therapy according to the following starting schedule:

Nivolumab starting approximately on day 24 \pm 2 days at a dose defined by Phase I portion of the study but it is expected that the dose 3 mg/kg will be selected based on prior studies.

Idarubicin 12 mg/m² IV over 15 to 30 minutes daily x 3 (days 1-3)

ara-C 1.5 g/m² IV over 24 hours daily (days 1-4) (days 1-3 for patients older than 60)

Solumedrol 50 mg or dexamethasone 10 mg IV daily for 3-4 days with ara-C (days 1-4) (days 1-3 for patients older than 60).

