 - Isolated Grade 4 amylase or lipase abnormalities that are not associated with symptoms or clinical manifestations of pancreatitis and decrease to < Grade 4 within 1 week of onset.
 - Isolated Grade 4 electrolyte imbalances/abnormalities that are not associated with clinical sequelae and are corrected with supplementation/appropriate management within 72 hours of their onset
- Any dosing interruption lasting > 6 weeks with the following exceptions:
 - Dosing interruptions to allow for prolonged steroid tapers to manage drug-related adverse events are allowed. Prior to re-initiating treatment in a subject with a dosing interruption lasting > 6 weeks, the Investigator must be consulted. Tumor assessments should continue as per protocol even if dosing is interrupted
 - Dosing interruptions > 6 weeks that occur for non-drug-related reasons may be allowed if approved by the Investigator. Prior to re-initiating treatment in a subject with a dosing interruption lasting > 6 weeks, the Investigator must be consulted. Tumor assessments should continue as per protocol even if dosing is interrupted
- Any adverse event, laboratory abnormality, or intercurrent illness which, in the judgment of the Investigator, presents a substantial clinical risk to the subject with continued nivolumab dosing

5.11

Definition of Dose Limiting Toxicity (DLT)

Dose-Limiting Toxicity will be graded according to the NCI Common Toxicity Criteria version4.03. See NCI Common Toxicity Criteria for definitions of DLT by organ system.

- a) All \geq grade 3 drug-related, clinically significant non-hematologic toxicities will be considered DLTs. A study drug-related occurrence of an elevation in AST/ALT $> 3 \times$ ULN and concomitant Bilirubin of $> 2 \times$ ULN is a Dose Limiting Toxicity and patients meeting this criteria should be permanently discontinued from study treatment (nivolumab).
As the following are common events in patients with leukemia (> 50%), they will not be used for the definition of MTD and DLT, nor will they be reported as ADRs: low blood pressure due to dehydration requiring fluid replacement, abnormalities of LDH (lactate dehydrogenase) and alkaline phosphatase, disturbances in electrolytes (magnesium, phosphorus,

calcium), alopecia, nausea and vomiting (if manageable with supportive care measures).

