b) Grade 3 hematologic toxicity (criteria for leukemia on the CTC version 3.0) lasting for 6 weeks or more after interruption of therapy with a hypocellular bone marrow and no marrow blasts. Anemia will not be considered a hematologic DLT. As the following are common events in patients with leukemia (> 50%), they will not be used for the definition of MTD and DLT, nor will they be reported as ADRs: prolonged myelosuppression (grade 3 - 4), neutropenic fever without infection (grade 3), non-neutropenic fever (grade 3), infections with grade 3 and 4 neutropenia, infections without neutropenia (grade 3), readmission associated with NCI grade 3 toxicity cytopenias not resulting in death, transfusions of platelets and packed RBCs (grade 3).

5.12

Concomitant medications: In the event of severe anemia, thrombocytopenia or neutropenia, patients may receive appropriate supportive care (e.g., transfusions, prophylactic antibiotics, antifungals and/or antivirals, hematopoietic growth factors). In the event of high white blood cell (WBC) counts, patients may receive hydroxyurea (at any dose) or 1 dose of cytarabine (up to \leq 2g) prior to start of study treatment in order to keep their WBC at an acceptable level while being evaluated for the study. During the trial they may undergo leukopheresis for the same purpose.

Concomitant administration of any other therapy specific for MDS or AML, including any use of systemic retinoids, is prohibited. Concomitant administration of any other anticancer therapy is prohibited. Intrathecal chemotherapy is allowed, when indicated.

Subjects may receive anti-infective prophylaxis according to institutional practices. Use of recombinant myeloid colony stimulating factors (CSF) is allowed, if patients have febrile neutropenia or documented infections.

Concomitant medications will be recorded in the medical records only.

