10.0 Reporting of Adverse Events

These guidelines serve to bring the Department of Leukemia in compliance with the institutional policy on Reporting of Serious Adverse Events.

Adverse event is any untoward medical occurrence that may present during treatment with a pharmaceutical product but which does not necessarily have a causal relationship with this treatment. Adverse drug reaction is a response to a drug which is noxious and unintended and which occurs at doses normally used in man for prophylaxis, diagnosis, or therapy of disease or for the modification of physiologic function.

Assessing causal connections between agents and disease is fundamental to the understanding of adverse drug reactions. In general, a drug may be considered a contributory cause of an adverse event if, had the drug not been administered, 1) the event would not have happened at all, 2) the event would have occurred later than it actually did, or 3) the event would have been less severe.

Only unexpected AEs related to leukemia and events resulting in dose modification/delay will be recorded in the Case Report Form (CRF).

Expected events during leukemia therapy are:

- Myelosuppression related events (due to disease or leukemia therapy)
- Febrile or infection episodes not requiring management in the intensive care unit
- Epistaxis or bleeding except for catastrophic CNS or pulmonary hemorrhage
- Anemia, neutropenia, lymphopenia, thrombocytopenia, leukopenia
- Disease related events
- Symptoms associated with anemia (fatigue, weakness, shortness of breath)
- Electrolyte abnormalities (sodium, potassium, bicarbonate, CO₂, magnesium)
- Chemistry abnormalities (LDH, phosphorus, calcium, BUN, protein, albumin, uric acid, alkaline phosphatase, glucose)
- Coagulation abnormalities
- Disease specific therapy (induction, maintenance, salvage, or stem cell therapy)

- Alopecia
- Bone, joint, or muscle pain
- Disease progression
- Abnormal hematologic values
- General therapy related events
- Catheter related events
- Renal failure related to tumor lysis syndrome or antibiotic/ antifungal therapy
- Rash related to antibiotic use
- Hospitalization for the management of any of the above expected events
- Abnormal hematologic values will not be recorded on the case report form. For abnormal chemical values, the apogee or nadir (whichever is appropriate) will be reported per course on the case report form.

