12.2 Phase I study

The 3+3 design will be used to identify the MTD of nivolumab. The following table lists out the 3 dosage levels that will be used in the study, and the starting dose is 1mg/kg IV

of Nivolumab With 3 doses, the maximum total number of patients for phase I part will be 12 patients.

The dose of treatment agent, that is, Nivolumab, will be escalated in successive cohorts of patients. Patients will be entered sequentially to each dose level. If none of the first 3 patients at a dose level experience first cycle dose-limiting toxicity (DLT), new patients may be entered at the next higher dose level. If 1 of 3 patients experience first cycle DLT, up to 3 more patients are started at that same dose level. If 1 of 6 experience DLT, then new patients may be entered at the next higher dose level. If 2 or more experience first cycle DLT, no further patients are started at that dose. The MTD is the highest dose level in which <2 patients of 6 develop first cycle DLT.

Table 13.1 Dose levels of nivolumab

Dose level	Nivolumab (mg/kg IV)
-1	0.3
0	1
1	3

Prior to advancing/changing dose levels, a cohort summary will be completed and submitted to the IND Office Medical Monitor for review and approval.

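### The DLT exclusion for neutropenic infection in section 5.11 b has no severity limit, so a fatal first-cycle case attributed to nivolumab is not counted as a DLT

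*Combined protocol and SAP*

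**What the plan says.** Section 5.11 defines the DLT in two items. Item a is the general rule for events of grade 3 or higher: "drug-related, clinically significant non-hematologic toxicities will be considered DLTs". It sets no upper grade.

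Each item then gives a list of exclusions, introduced by the same sentence: "As the following are common events in patients with leukemia (> 50%), they will not be used for the definition of MTD and DLT". The list in item b includes "infections with grade 3 and 4 neutropenia, infections without neutropenia (grade 3), readmission associated with NCI grade 3 toxicity cytopenias not resulting in death".

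The DLT count drives phase I. Section 12.2 states: "If 1 of 3 patients experience first cycle DLT, up to 3 more patients are started at that same dose level". With no DLT in 3, or with 1 in 6, the next level may open; with 2 or more, the level closes. The dose carried forward is bounded by the same count: "The MTD is the highest dose level in which <2 patients of 6 develop first cycle DLT". Section 12.2 also requires a cohort summary and the Medical Monitor's approval before any change of dose level.

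On timing, the phase I schedule in section 5.2 reads "Nivolumab dosed as indicated below starting approximately on day 24", with a margin of 2 days either way, in a cycle of about 28 to 35 days. Each cohort is "observed for approximately 3 weeks from the first dose of Nivolumab" before the next one opens.

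**The concern.** The neutropenic-infection entry is the only infection or fever entry in the 5.11 b list without a limit on the event itself. The list is justified by frequency: its events are said to occur in more than half of leukemia patients. That describes ordinary infection after induction chemotherapy. It does not describe a death that the investigator has attributed to the study drug.

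In a 3+3 design with at most 12 patients, one event decides whether a cohort expands, and two decide whether a level closes. If a treatment-related death is left out by definition, the formal count can permit escalation, or certify an MTD, that it would otherwise have blocked.

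**Working it through.** **1. Entries side by side (section 5.11 b)**

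| Excluded event | Limit on the event |
|---|---|
| Neutropenic fever without infection | grade 3 |
| Fever without neutropenia | grade 3 |
| Infection without neutropenia | grade 3 |
| Readmission with grade 3 cytopenias | must not end in death |
| Infection with grade 3 and 4 neutropenia | none; the grades describe the neutropenia |

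The words about death belong to the readmission entry. They do not reach back to infection.

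**2. Which item governs.** Item a speaks of all such toxicities and then removes some non-hematologic ones itself, such as manageable nausea and vomiting. The general rule is therefore subject to the exclusion lists. Item b uses the same exclusion sentence and does not confine it to the hematologic criterion. The specific exclusion prevails, and the list has no exception for attribution to nivolumab.

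**3. Effect on the 3+3 count**

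| Case | As written | If the death counted |
|---|---|---|
| One such death in the first 3, no other DLT | 0/3, next level may open | 1/3, up to 3 more at this dose |
| One other DLT in the first 3, one such death in the second 3 | 1/6, meets the MTD bound | 2/6, fails the bound and closes the level |

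**4. First-cycle window after the first nivolumab dose.** Nivolumab starts on day 22 to 26 of a 28 to 35 day cycle. Shortest: 28 - 26 = 2 days. Longest: 35 - 22 = 13 days. The cohort observation period gives about 21 days. Sections 13.2.5 and 13.3.5 put count recovery at days 21 to 28, so neutropenia can overlap the first dose.

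**5. Illustration only.** The documents give no rate for this event. Let q be an assumed first-cycle rate per patient, with no other DLTs:

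- At least one in 3: 1 - (1-q)^3
- Expansion from 3 to 6: 3q(1-q)^2
- Level cleared: (1-q)^3 + 3q(1-q)^2 × (1-q)^3
- Level closed: 1 minus the line above
- Two or more in 6: 1 - (1-q)^6 - 6q(1-q)^5

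| If such deaths counted | q = 2% | q = 5% | q = 10% |
|---|---|---|---|
| At least one in 3 | 0.059 | 0.143 | 0.271 |
| Cohort expands to 6 | 0.058 | 0.135 | 0.243 |
| Level cleared | 0.995 | 0.973 | 0.906 |
| Level closed | 0.005 | 0.027 | 0.094 |
| Two or more in 6 | 0.006 | 0.033 | 0.114 |

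For example, at q = 5%: 0.95^3 = 0.857; 3 × 0.05 × 0.95^2 = 0.135; cleared = 0.857 + 0.135 × 0.857 = 0.973. As the section is written, these deaths contribute nothing, so with no other DLTs every level clears whatever q is. The 10% column is an illustrative upper end, not an expectation.

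**The case against.** **The exclusion has a reason.** Infection during neutropenia is an expected effect of idarubicin and cytarabine, and section 5.6 says that nivolumab is not associated with myelosuppression. Section 2.1 reports 22% induction mortality (54 of 245) in patients aged 65 or older. That figure is all-cause and covers 7 weeks, so it is not the rate at issue, but it shows a substantial background. With 3 to 6 patients per level, counting chemotherapy deaths could close a dose for the wrong reason. This stands as a reason to keep ordinary neutropenic infection excluded. It does not justify excluding a death attributed to nivolumab.

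**The safeguards are real.** Under section 10 all SAEs go to the IND Office within 5 working days, and to the drug supplier within 24 hours. Unexpected, related fatal events need a written report within 24 hours. Escalation is permissive and needs Medical Monitor approval. A reader might infer that the trial could escalate past such a death unnoticed; the documents do not support that. What remains is that none of these steps adds a DLT criterion or changes the MTD bound.

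**Is there an unresolved conflict between 5.11 a and 5.11 b?** A reader might infer one, since a covers all such toxicities and b removes this one. The text does not support that, for the reason in step 2 of the working. A reader might also take the b list to limit only the hematologic criterion, so that the death counts under a. The exclusion sentence has no such restriction.

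**Section 10.0 is weak support.** It treats as expected "Febrile or infection episodes not requiring management in the intensive care unit", which shows a severity limit on infection elsewhere in the protocol. But that list governs recording on the case report form, not DLTs, and it also includes myelosuppression-related events without any limit.

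**Conclusion.** The point holds as a minor one. As written, a fatal first-cycle infection with grade 3-4 neutropenia attributed to nivolumab is outside the DLT count. Per event the size is exact: 0/3 instead of 1/3, or 1/6 instead of 2/6.

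The expected effect is small. The event must be infectious, fatal, accompanied by grade 3-4 neutropenia, attributed to nivolumab and within the first cycle, in at most 12 patients. The probabilities rest on assumed rates and on there being no other DLTs; they should not be read as estimates.

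The mismatch with the common-event reason suggests a drafting gap rather than an intention to ignore deaths, but the wording has the effect described. A reader might extend the point to the phase II toxicity stopping rule, because it names grades 3 and 4. That is a separate rule, does not define the phase I DLT, and does not bear on this point.

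**What to change.** In section 5.11 b, add a parenthesis to the neutropenic-infection entry: *(not resulting in death)*. Then add one sentence: *A fatal infection with grade 3-4 neutropenia in the first cycle that is attributed to nivolumab is a DLT.*

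The parenthesis borrows the limit already used for readmission. Attribution can use the drug-specific relationship that section 10.0 already requires in the toxicity log and case report form, so no new data are needed. Non-fatal neutropenic infections stay excluded. Whether grade 4 infections should also count is a clinical choice for the study team.

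The cost is an occasional extra DLT. It may expand a cohort to 6 or, with a second DLT, close a level, including when an infection really caused by chemotherapy is attributed to nivolumab.

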6.0 Protocol Summary/Schema

6.1 Proposed Study

We propose to investigate the combination of idarubicin, cytarabine and nivolumab in patients with high-risk MDS and AML. In the phase I portion of the trial, the aim is to determine the tolerability of the combination. In the phase II

portion of the trial, the event free survival in newly diagnosed patients with AML and high-risk MDS ($\geq 10\%$ blasts) will be determined.

Schedule of Evaluations/ Study Calendar							
(refer to section 7.0 - 8.0 of protocol body)							
Parameter	Prestudy	Weeklyx4 During first course	Induction phase every 4-7 days	Induction phase every 1-2 weeks	Consolidation Maintenance phase every 1-4 wks	Consolidation Maintenance phase every 4-8 wks	End of Study
H&P	X	X					X
Weight/BP	X						
CBC, diff+platelet	X	X	X		X		
Chemistry+Coag:							
total bili	X	X		X		X	
creatinine	X	X		X		X	
SGPT	X	X		X		X	
PT/PTT/INR	X			X		X	
TSH	X						
pregnancy test***	X						
BMA****	X						
Echo/Muga	X						
MRD****	X						
Correlative studies: see section 16							

*** Blood or Urine pregnancy test on women of childbearing potential

****Bone Marrow Aspirate Pre-Treatment - within one month with cytogenetics and molecular studies if not done before. On-Study: BMA + cytogenetics and molecular studies (if abnormal at start) on day 21-28, then every 1-2 wks as required until CR. Then every 3-6 months. X 1 year. May be omitted in patients with clear evidence of active disease (see section 8.2).

Minimal residual disease (MRD) studies by flow cytometry to be performed on pre-treatment bone marrow and all subsequent bone marrow exams

7.0 Pretreatment Evaluation

- 7.1 History and physical examination, weight, BP.
- 7.2 CBC, platelet count, differential, creatinine, total bilirubin, SGPT, PT, PTT, INR, TSH.
Serum or urine pregnancy test for women of childbearing potential.
- 7.3 Bone marrow aspirate for morphology (within one month) and cytogenetics and molecular studies (if not done before).
- 7.4 Blood samples (10cc)/bone marrow, optional, for correlative studies.
- 7.5 Echocardiogram or MUGA scan.

8.0 Evaluation During Study

- 8.1 CBC, platelet, differential (if WBC $> 10^9/L$) every 4-7 days during remission induction and every 1 to 4 weeks during maintenance therapy.
- 8.2 Bone marrow aspirate and cytogenetics and molecular studies (if abnormal at start) on day 21-28; then aspirate every 1-2 weeks as required until CR; then every 3-6 months in year 1 if deemed necessary by the treating physician. Bone marrow aspiration may be omitted in patients where there is clear evidence of active disease (e.g., persistent blasts in peripheral blood).
- 8.3 Creatinine, total bilirubin and SGPT, PT, PTT, and INR every 1-2 weeks during induction then every 4-8 weeks on study.
- 8.4 Blood samples (10cc)/bone marrow (optional studies, see Section 14)
- 8.5 End of Study: History and physical exam
End of study evaluation will be performed after the completion of the maintenance therapy, or any time before that if the patient withdraws from the study or the treatment is discontinued for toxicity or disease relapse/progression.

9.0 Criteria for Response and Toxicity

- 9.1 Responders are patients who obtain a CR or PR, with or without cytogenetic response, or CRp (i.e., CR except for platelet counts $< 100 \times 10^9/L$ but not requiring platelet transfusions).

- 9.2 **Definitions**

- a. Complete Response (CR): Normalization of marrow ($\leq 5\%$ blasts and of peripheral blood counts (neutrophil count $\geq 10^9/L$, platelet count $> 100 \times 10^9/L$).
- b. Partial response (PR): as for CR but with reduction of marrow blasts by $>50\%$ and to $<10\%$.
- c. CRp = CR, but platelets $<100 \times 10^9/L$.
- d. Progressive disease: increase of blasts to $\geq 10\%$ after an initial response.

10.0 Reporting of Adverse Events

These guidelines serve to bring the Department of Leukemia in compliance with the institutional policy on Reporting of Serious Adverse Events.

Adverse event is any untoward medical occurrence that may present during treatment with a pharmaceutical product but which does not necessarily have a causal relationship with this treatment. Adverse drug reaction is a response to a drug which is noxious and unintended and which occurs at doses normally used in man for prophylaxis, diagnosis, or therapy of disease or for the modification of physiologic function.

Assessing causal connections between agents and disease is fundamental to the understanding of adverse drug reactions. In general, a drug may be considered a contributory cause of an adverse event if, had the drug not been administered, 1) the event would not have happened at all, 2) the event would have occurred later than it actually did, or 3) the event would have been less severe.

Only unexpected AEs related to leukemia and events resulting in dose modification/delay will be recorded in the Case Report Form (CRF).

Expected events during leukemia therapy are:

- Myelosuppression related events (due to disease or leukemia therapy)
- Febrile or infection episodes not requiring management in the intensive care unit
- Epistaxis or bleeding except for catastrophic CNS or pulmonary hemorrhage
- Anemia, neutropenia, lymphopenia, thrombocytopenia, leukopenia
- Disease related events
- Symptoms associated with anemia (fatigue, weakness, shortness of breath)
- Electrolyte abnormalities (sodium, potassium, bicarbonate, CO₂, magnesium)
- Chemistry abnormalities (LDH, phosphorus, calcium, BUN, protein, albumin, uric acid, alkaline phosphatase, glucose)
- Coagulation abnormalities
- Disease specific therapy (induction, maintenance, salvage, or stem cell therapy)

- Alopecia
- Bone, joint, or muscle pain
- Disease progression
- Abnormal hematologic values
- General therapy related events
- Catheter related events
- Renal failure related to tumor lysis syndrome or antibiotic/ antifungal therapy
- Rash related to antibiotic use
- Hospitalization for the management of any of the above expected events
- Abnormal hematologic values will not be recorded on the case report form. For abnormal chemical values, the apogee or nadir (whichever is appropriate) will be reported per course on the case report form.

All events that are not listed as expected in section 10.0 will be collected for the purpose of grading, and determining attribution to study drug by the PI.

All grade 3 and greater non-hematological events that are felt to be related to protocol treatment drugs will be documented on the toxicity log and entered into the case report form. The toxicity log and case report form data must reflect relationship to the drug the event is felt to be related to.

An adverse event or suspected adverse reaction is considered “serious” if, in the view of either the investigator or the sponsor, it results in any of the following outcomes:

- Death
- A life-threatening adverse drug experience – any adverse experience that places the patient, in the view of the initial reporter, at immediate risk of death from the adverse experience as it occurred. It does not include an adverse experience that, had it occurred in a more severe form, might have caused death.
- Inpatient hospitalization or prolongation of existing hospitalization
- A persistent or significant incapacity or substantial disruption of the ability to conduct normal life functions.
- A congenital anomaly/birth defect.

Important medical events that may not result in death, be life-threatening, or require hospitalization may be considered a serious adverse drug experience when, based upon appropriate medical judgment, they may jeopardize the patient or subject and may require medical or surgical intervention to prevent one of the outcomes listed in this definition.

Examples of such medical events include allergic bronchospasm requiring intensive treatment in an emergency room or at home, blood dyscrasias or convulsions that do not result in inpatient hospitalization, or the development of drug dependency or drug abuse (21 CFR 312.32).

- **Important medical events as defined above, may also be considered serious adverse events. Any important medical event can and should be reported as an**

SAE if deemed appropriate by the Principal Investigator or the IND Sponsor, IND Office.

- All events occurring during the conduct of a protocol and meeting the definition of a SAE must be reported to the IRB in accordance with the timeframes and procedures outlined in “The University of Texas M. D. Anderson Cancer Center Institutional Review Board Policy for Investigators on Reporting Unanticipated Adverse Events for Drugs and Devices”. Unless stated otherwise in the protocol, all SAEs, expected or unexpected, must be reported to the IND Office, regardless of attribution (within 5 working days of knowledge of the event).
- **All life-threatening or fatal events**, that are unexpected, and related to the study drug, must have a written report submitted within **24 hours** (next working day) of knowledge of the event to the Safety Project Manager in the IND Office.
- Unless otherwise noted, the electronic SAE application (eSAE) will be utilized for safety reporting to the IND Office and MDACC IRB.
- Serious adverse events will be captured from the time of the first protocol-specific intervention, until 30 days after the last dose of drug, unless the participant withdraws consent. Serious adverse events must be followed until clinical recovery is complete and laboratory tests have returned to baseline, progression of the event has stabilized, or there has been acceptable resolution of the event.
- Additionally, any serious adverse events that occur after the 30 day time period that are related to the study treatment must be reported to the IND Office. This may include the development of a secondary malignancy.

Reporting to the FDA:

- Serious adverse events will be forwarded to FDA by the IND Sponsor (Safety Project Manager IND Office) according to 21 CFR 312.32.

It is the responsibility of the PI and the research team to ensure serious adverse events are reported according to the Code of Federal Regulations, Good Clinical Practices, the protocol guidelines, the sponsor's guidelines, and Institutional Review Board policy.

The investigator or physician designee is responsible for verifying and providing source documentation for all adverse events and assigning the attribution for each event for all subjects enrolled on the trial.

Adverse events and protocol specific data will be entered into PDMS/CORe and PDMS/CORe will be used as the electronic case report form for this protocol.

10.1 Adverse Events Requiring Expedited Reporting:

Bristol Meyers-Squibb Adverse Event Reporting:

Serious adverse events (SAEs) considered associated with therapy should be reported to the Principal Investigator within 48 hours of observing or learning of the event. All AEs should be reported to the research nurse. The principal investigator, in turn, will be responsible for reporting the event to the IRB.

All Serious Adverse Events must be reported to BMS Worldwide Safety

- All SAEs, whether related or unrelated to Nivolumab and all pregnancies must be reported to BMS (by the investigator or designee) within 24 hours.
- All SAEs should be reported via confirmed facsimile (fax) transmission, or scanned and reported via electronic mail to:

SAE Email Address: [contact]

SAE [contact]

Serious Adverse Event (SAE): any untoward medical occurrence at any dose (including overdose) that:

- a. Results in death (caused or led to death); or
- b. Is life-threatening (placed the subject at immediate risk or death); and/or
- c. Requires or prolongs inpatient hospitalization (elective medical/surgical procedures, scheduled therapies, or routine check-ups excluded); and/or
- d. Is disabling (substantial disruption of the subject's ability to carry out normal life functions); and/or
- e. Is a congenital anomaly/birth defect (adverse outcome in a child or fetus of a subject exposed to a medicinal product prior to conception or during pregnancy); or
- f. Does not meet any of the above serious criteria but may jeopardize the subject and may require medical or surgical intervention to prevent one of the outcomes listed above.

Associated Adverse Event:

- a. If there is a clinically plausible time sequence between the onset of the AE and administration of therapy; and/or
- b. If there is a biologically plausible mechanism for therapy causing or contributing to the AE; and the AE may or may not be attributed to concurrent/underlying illnesses, other drugs, or procedures.

10.3 **CTCAE term (AE description) and grade:** The descriptions and grading scales found in the revised NCI Common Terminology Criteria for Adverse Events (CTCAE) version 4.03 will be utilized for AE reporting. All

appropriate treatment areas should have access to a copy of the CTCAE version 4.03. A copy of the CTCAE version 4.03 can be downloaded from the CTEP web site (<http://ctep.cancer.gov>).

‘Expectedness’: AEs can be ‘Unexpected’ or ‘Expected’ for expedited reporting purposes only. ‘Expected’ AEs (the ASAEL) are ***bold and italicized*** in the CAEPR.

Attribution of the AE:

- Definite – The AE is *clearly related* to the study treatment.
- Probable – The AE is *likely related* to the study treatment.
- Possible – The AE *may be related* to the study treatment.
- Unlikely – The AE is *doubtfully related* to the study treatment.
- Unrelated – The AE is *clearly NOT related* to the study treatment.

10.4 All safety reports, including SADRs, shall be sent electronically to [contact] or by fax to [contact] to the attention of one of the Bayer Drug Safety Assurance contacts listed below: The Principal Investigator commits to respond promptly to any query from Bayer regarding SADR reports.

